8. RESEARCH QUESTION AND OBJECTIVES

Hypothesis

There are not hypotheses to evaluate.

Research Question

What is the impact of tafamidis use in Colombian patients diagnosed with ATTR-CM on quality of life during two years of follow-up?

Primary objective

To describe the impact of tafamidis use in Colombian patients diagnosed with ATTR-CM on quality of life during two years of follow-up

Secondary objectives

- To describe the clinical and demographic characteristics of the patients at the moment of prescription of tafamidis
- To determine the treatment patterns to manage ATTR-CM before tafamidis prescription
- To evaluate the frequency of hospitalization and its causes during the follow-up period
- To describe the use of cardiovascular devices during follow-up of patients recruited in the study
- To outline the change in baseline for patients in cardiovascular functionality in patients prescribed tafamidis
- To measure the adherence of the patients to the therapy
- To describe the access barriers during the use of tafamidis

Exploratory objectives

- To analyze the relationship between baseline variables and patient and changes of quality of life and cardiovascular functionality

PFIZER CONFIDENTIAL

CT24-WI-GL02-RF01 6.0 Non-Interventional Study Protocol Template For Primary Data Collection Study 01-Aug-2023
Page 20 of 57

CLINICAL AND MEDICAL CONTROLLED DOCUMENT (CMCD) REQUIRED FORM/TEMPLATE

Identifier	Version	Title	Effective Date
CT24-WI-GL02-RF01	6.0	NON-INTERVENTIONAL STUDY PROTOCOL TEMPLATE FOR PRIMARY DATA COLLECTION STUDY	01-Aug-2023

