9.3. Variables

Table 2 List of variables

Variable	Role	Data source(s)	Operational definition
Date of birth	Demographic characteristics	Medical record, Interview	dd-mm-yyyy
Age	Demographic characteristics	Medical record, Interview	Time elapsed since the time of birth to signed consent form (years)
Sex assigned at birth	Demographic characteristics	Medical record, Interview	Men, female
Race (ethnicity)	Demographic characteristics	Medical record, Interview	Indigenous, Rrom, Black, None and Other
Date of symptoms of ATTR-CM	Clinical characteristic	Medical record, Interview	dd-mm-yyyy
Date of ATTR-CM diagnosis	Clinical characteristic	Medical record, Interview	dd-mm-yyyy
Genotype	Clinical characteristic	Medical record, Interview	ATTRwt; ATTRv
Scintigraphy at diagnosis (Perugini scale)	Clinical characteristic	Medical record,	Grade 0 – 3
Biopsy	Clinical characteristic	Medical record, Interview	Yes, No
Sampling biopsy	Clinical characteristic	Medical record, Interview	Heart, bone marrow, others
Sum of QRS amplitude in I, II, and III leads at diagnosis	Clinical characteristic	Medical record, Interview	mm
Sum of QRS amplitude in all six limb leads at diagnosis	Clinical characteristic	Medical record, Interview	mm
Sum of QRS amplitude in all six precordial leads at diagnosis	Clinical characteristic	Medical record, Interview	mm
Sokolow-Lyon index low voltage criteria at diagnosis	Clinical characteristic	Medical record, Interview	mm
Low QRS voltage at diagnosis	Clinical characteristic	Medical record, Interview	Yes, No

PFIZER CONFIDENTIAL

CT24-WI-GL02-RF01 6.0 Non-Interventional Study Protocol Template For Primary Data Collection Study 01-

Aug-2023

Page 24 of 57

**CLINICAL AND MEDICAL CONTROLLED DOCUMENT (CMCD)
REQUIRED FORM/TEMPLATE**

Identifier	Version	Title	Effective Date
CT24-WI-GL02-RF01	6.0	NON-INTERVENTIONAL STUDY PROTOCOL TEMPLATE FOR PRIMARY DATA COLLECTION STUDY	01-Aug-2023

Pseudo-infarct Q waves at diagnosis	Clinical characteristic	Medical record, Interview	Yes, No
Atrioventricular conduction disease (block) at diagnosis	Clinical characteristic	Medical record, Interview	Yes, No
Genetic counseling	Patient	Medical record, Interview	Yes, No
Left ventricular ejection fraction at diagnosis	Clinical characteristic	Medical record, Interview	%
N-terminal pro b-type natriuretic peptide at diagnosis	Clinical characteristic	Medical record, Interview	(pg/mL)
Heart failure at early age	Clinical characteristic	Medical record, Interview	Yes, No

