Any cardiac arrhythmias or conduction disorders	Clinical characteristic	Medical record, Interview	Yes, No
Type of any cardiac arrhythmias or conduction disorders	Clinical characteristic	Medical record, Interview	Cardiac arrhythmias, Cardiac arrest, Paroxysmal tachycardia, Atrial fibrillation and flutter, Conduction disorders, Atrioventricular and left bundle branch block, other conduction disorders
Lumbar spinal stenosis	Clinical characteristic	Medical record, Interview	Yes, No
Hypertrophic cardiomyopathy over 60 years old	Clinical characteristic	Medical record, Interview	Yes, No
Embolic stroke	Clinical characteristic	Medical record, Interview	Yes, No
Low flow/low gradient aortic valve stenosis	Clinical characteristic	Medical record, Interview	Yes, No
Diabetes mellitus	Clinical characteristic	Medical record, Interview	Yes, No
Hypertension	Clinical characteristic	Medical record, Interview	Yes, No
Sleep apnea	Clinical characteristic	Medical record, Interview	Yes, No
Chronic Kidney Diseases	Clinical characteristic	Medical record, Interview	Yes, No
Any cardiovascular device	Clinical characteristic	Medical record, Interview	Yes, No
Which any cardiovascular devices	Clinical characteristic	Medical record, Interview	Cardiac resynchronization

PFIZER CONFIDENTIAL

CT24-WI-GL02-RF01 6.0 Non-Interventional Study Protocol Template For Primary Data Collection Study 01-

Aug-2023

Page 25 of 57

**CLINICAL AND MEDICAL CONTROLLED DOCUMENT (CMCD)
REQUIRED FORM/TEMPLATE**

Identifier	Version	Title	Effective Date
CT24-WI-GL02-RF01	6.0	NON-INTERVENTIONAL STUDY PROTOCOL TEMPLATE FOR PRIMARY DATA COLLECTION STUDY	01-Aug-2023

			therapy – defibrillator (CRT-D), Cardiac resynchronization therapy – pacemakers (CRT-P), implantable cardioverter defibrillator (ICD)
History of heart block	Clinical characteristic	Medical record, Interview	Yes, No
NYHA FC	Clinical characteristic	Medical record, Interview	I, II, III, IV
Syncope	Clinical characteristic	Medical record, Interview	Yes, No
Carpal tunnel syndrome	Clinical characteristic	Medical record, Interview	Yes, No
Bleeding history	Clinical characteristic	Medical record, Interview	Yes, No
Intracardiac thrombosis	Clinical characteristic	Medical record, Interview	Yes, No
Stroke	Clinical characteristic	Medical record, Interview	Yes, No
Polyneuropathy	Clinical characteristic	Medical record, Interview	Yes, No
Orthostatic hypotension	Clinical characteristic	Medical record, Interview	Yes, No

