Cardiovascular devices during follow-up	Treatment	Medical record, Interview	Cardiac resynchronization therapy – defibrillator (CRT-D), Cardiac resynchronization therapy – pacemakers (CRT-P), implantable cardioverter defibrillator (ICD)
Date of prescription of tafamidis	Treatment	Interview	ddmm/yyyy

PFIZER CONFIDENTIAL

CT24-WI-GL02-RF01 6.0 Non-Interventional Study Protocol Template For Primary Data Collection Study 01-

Aug-2023

Page 27 of 57

**CLINICAL AND MEDICAL CONTROLLED DOCUMENT (CMCD)
REQUIRED FORM/TEMPLATE**

Identifier	Version	Title	Effective Date
CT24-WI-GL02-RF01	6.0	NON-INTERVENTIONAL STUDY PROTOCOL TEMPLATE FOR PRIMARY DATA COLLECTION STUDY	01-Aug-2023

Date of first administration of tafamidis	Treatment	Interview	ddmm/yyyy
Delay of supply of tafamidis	Treatment	Interview	Yes, No
Cause of delay	Treatment	Interview	Authorization, Treatment not available in the supplier, error of prescription, other
Adherence	Outcomes	Interview	%
Sum of QRS amplitude in I, II, and III leads at the end of follow-up	Clinical characteristic	Medical record, Interview	mm
Sum of QRS amplitude in all six limb leads at the end of follow-up	Clinical characteristic	Medical record, Interview	mm
Sum of QRS amplitude in all six precordial leads at the end of follow-up	Clinical characteristic	Medical record, Interview	mm
Sokolow-Lyon index low voltage criteria at the end of follow-up	Clinical characteristic	Medical record, Interview	mm
Persistence	Outcomes	Interview	Yes, No
Hospitalization	Outcomes	Interview	Yes, No
Cause of the hospitalization	Outcomes	Interview	Cardiovascular, Other
Date of hospitalization	Outcomes	Interview	Date of admission: dd-mm-yyyy Date of discharge: dd-mm-yyyy
Day(s) of hospitalization	Outcomes	Interview	Days
Quality of life (KCCQ-OS score per visit)	Outcomes	Interview	Score
6MWT [§]	Outcomes	Site	Meters
Scintigraphy (Perugini scale) [§]	Outcomes	Site	Grade 0 - 3

* Per visits, according to schedule of the study

§ According to medical criteria, considering that the physician may choose to perform a different test

PFIZER CONFIDENTIAL

CT24-WI-GL02-RF01 6.0 Non-Interventional Study Protocol Template For Primary Data Collection Study 01-

Aug-2023

Page 28 of 57

**CLINICAL AND MEDICAL CONTROLLED DOCUMENT (CMCD)
REQUIRED FORM/TEMPLATE**

Identifier	Version	Title	Effective Date
CT24-WI-GL02-RF01	6.0	NON-INTERVENTIONAL STUDY PROTOCOL TEMPLATE FOR PRIMARY DATA COLLECTION STUDY	01-Aug-2023

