9.3.1. Definitions

Kansas City Cardiomyopathy Questionnaire (KCCQ) Score: It is a Patient-reported outcome composed by 23-item, KCCQ that takes 4-6 min to complete. A self-administered questionnaire will be used to measure the patient's perception of their health status within a 2-week recall period. The domains of this scale are: Symptom, Physical function, Social Limitation, self-efficacy, Symptom stability, and Quality of Life. The clinical summary is calculated including the domain Physical limitation and Symptoms. The overall summary score combines total symptoms, physical and social limitation, and Quality of life. The score for each domain has a range from 0-100 where 0 is considered worst health and 100 the best health. Changes in the Overall summary of 5, 10 and 20 points have been considered small but clinically important, moderate to large, and large to very large changes, respectively (12). The scale has been translated and validated to Spanish of Colombia (15).

Perugini grading scale: It is a semi-quantitative method of scoring cardiac uptake following injection of 99mTc-DPD, 99mTc-Pyrophosphate or 99mTc-HMDP scintigraphy (16). It is classified as:

- grade 0: no cardiac uptake and normal rib uptake
- grade 1: cardiac uptake which is less than rib uptake
- grade 2: cardiac uptake with intensity similar rib uptake
- grade 3: cardiac uptake greater than rib uptake with mild or absent rib uptake

6 Minute walk test: It is considered as an alternative to cardiopulmonary exercise test for risk stratification in patients with Heart Failure. It is a simple test that requires no specialized equipment or physicians. It assesses the functional capacity while the patient walks on a flat, solid surface in a period of 6 min (13).

Hospitalization: It is defined as a nonelective admission to an acute care setting for medical therapy that results in at least a 24-hour stay (17).

Cardiovascular causes of hospitalization: The following diseases were considered as cardiovascular causes of hospitalization only it was considered the primary diagnosis (17):

- Heart failure
- Arrhythmia: When the patient is hospitalized by bradyarrhythmia, atrial, or ventricular rhythm disorders of the heart.
- Transient ischemic attack
- Stroke

PFIZER CONFIDENTIAL

CT24-WI-GL02-RF01 6.0 Non-Interventional Study Protocol Template For Primary Data Collection Study 01-

Aug-2023

Page 29 of 57

**CLINICAL AND MEDICAL CONTROLLED DOCUMENT (CMCD)
REQUIRED FORM/TEMPLATE**

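### Table 2's device-type lists have no code for a conventional pacemaker or any other device, and the follow-up row cannot record that there is no device

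*Protocol*

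**What the plan says.** Section 8 lists this secondary objective: "To describe the use of cardiovascular devices during follow-up of patients recruited in the study". The variable that serves it is the follow-up device row of Table 2 (section 9.3). That row allows cardiac resynchronization therapy with "defibrillator (CRT-D), Cardiac resynchronization therapy – pacemakers (CRT-P), implantable cardioverter defibrillator (ICD"), and nothing else.

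The baseline device-type row has the same three values: "therapy – defibrillator (CRT-D), Cardiac resynchronization therapy – pacemakers (CRT-P), implantable cardioverter defibrillator (ICD"). It is preceded by a separate presence item: "Any cardiovascular device Clinical characteristic Medical record, Interview Yes, No". The follow-up row has no such item.

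Table 2 also collects "Atrioventricular conduction disease (block) at diagnosis" and "History of heart block Clinical characteristic Medical record, Interview Yes, No". Among the cardiovascular causes of hospitalization, section 9.3.1 defines arrhythmia thus: "When the patient is hospitalized by bradyarrhythmia, atrial, or ventricular rhythm disorders of the heart".

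**The concern.** A pacemaker without resynchronization is not a CRT-D, a CRT-P or an ICD. If a patient has one during follow-up, a site working from the list as written can leave the item empty or choose the nearest code, probably CRT-P. An empty item omits the device from the table. The nearest code puts it in the wrong row.

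The blank is ambiguous in its own right. Without a way to enter that there is no device, an empty follow-up field has three possible meanings: no device, a device outside the list, or information not obtained. Section 9.7.4 allows no imputation and says that missing data will be reported. A device frequency therefore needs a denominator of patients with known status, and the row as defined does not supply one.

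At stake is whether one secondary descriptive table is correct. The primary quality-of-life objective is not touched. The gap needs closing at data collection, because an analysis plan cannot recover a category that was never recorded.

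**Working it through.** **1. Is the list closed?** The protocol states no device rate, so there is no figure to reproduce. The check is whether any other part of the protocol widens the list.

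| Place | Device content |
|---|---|
| Section 2, abbreviations | CRT-D, CRT-P and ICD; pacemakers appear only within CRT-P |
| Section 4, abstract | Names the device variables, gives no further types |
| Table 2, baseline presence | Yes or No |
| Table 2, baseline type | CRT-D, CRT-P, ICD |
| Table 2, follow-up | CRT-D, CRT-P, ICD; no Yes/No, none or other |
| Section 9.3.1, definitions | No device definition |

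Nothing adds a conventional pacemaker or an open category.

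**2. Does Table 2 use open categories elsewhere?** Yes. The cause of a tafamidis supply delay is coded "Authorization, Treatment not available in the supplier, error of prescription, other", and the biopsy-site list also ends with an open category. The device rows do not follow that pattern.

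**3. Is a device outside the list foreseeable?** The protocol records atrioventricular block at diagnosis and history of heart block, and it counts bradyarrhythmia admissions. It therefore expects conduction disease in this cohort. It does not say which devices such patients receive. That a conventional pacemaker is among them is general clinical knowledge.

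**4. What is lost at each time point?**
- Baseline: a patient with a conventional pacemaker can be entered as Yes on presence. Only the type is lost or miscoded.
- Follow-up: both presence and type depend on the three-code row, so both can be lost.

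**5. Illustrative scale.** Inputs: n = 50, from section 9.5 (close to fifty), with n = 40 as a lower case because section 9.2 expects fewer than 50. The share p with a device outside the list is assumed. Expected number = n × p. Chance of at least one such patient = 1 − (1 − p)^n.

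| p (assumed) | n = 50: expected | n = 50: at least one | n = 40: expected | n = 40: at least one |
|---|---|---|---|---|
| 2% | 1 | 1 − 0.98^50 = 64% | 0.8 | 55% |
| 5% | 2.5 | 1 − 0.95^50 = 92% | 2 | 87% |
| 10% | 5 | 1 − 0.90^50 = 99.5% | 4 | 98.5% |

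Each misrecorded patient moves a device frequency by 1/50 = 2 percentage points.

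**The case against.** The strongest reply is that Table 2 gives short operational definitions and is not the CRF. Other rows also leave out a none option: anticoagulation after diagnosis lists four drugs, and the arrhythmia-type row lists only types. Section 9.1 has the CRF validated at two centres, including the definition of variables, and section 9.8 provides for queries on inconsistent or missing data. This has some force for the missing none, which may be shorthand. It does not answer the missing pacemaker and open categories. Those steps may catch the gap, but they add no code, and the definition that the protocol fixes is closed.

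It is also fair to say that the link from heart block to a conventional pacemaker is not in the protocol and that no frequency is given. That stands. It makes the undercount conditional on at least one such patient.

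A reader might infer four stronger things that the protocol does not support:
- **Every conventional pacemaker would vanish.** The baseline Yes/No item keeps presence.
- **New implants cannot be told from devices already in place.** Comparing baseline with follow-up identifies a new device when baseline is No or the recorded type differs. Doubt remains for same-type replacements and uncoded devices. The objective is also about use during follow-up, and a device already in place is in use.
- **The device subgroup in section 9.7.3.2 is spoiled.** The section does not say that the split is by type, and a split on baseline presence would survive.
- **Large numbers are affected.** A share of 10% to 30%, or 5 to 15 of 50 patients, could be supposed, but it has no source in the protocol. If it mixes baseline with follow-up devices, it also counts patients whose device presence is still recorded.

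**Conclusion.** The point holds in a limited form. Both device-type lists are closed to three codes, and nothing elsewhere in the protocol opens them. During follow-up, where a secondary objective depends on the row, a device outside the list would be omitted or miscoded, and a blank cannot be interpreted. At baseline the loss is confined to device type.

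The size cannot be derived from the protocol. On an assumed share of 2% to 10% of about 50 patients, about 1 to 5 patients would be affected, or 2 to 10 percentage points of a device frequency. The conclusion rests on two things from outside the protocol: that assumed share, and the general knowledge that conventional pacemakers are used in patients with conduction disease. That the lists are incomplete depends on neither. The change should be made because it is cheap and makes the device table interpretable. No conclusion about the primary objective depends on it.

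**What to change.** In Table 2 and the CRF:
- Add a conventional pacemaker code and an other category with free-text specification to both device-type rows, baseline and follow-up.
- Add a Yes/No presence item, or a none option, to the follow-up row, so that absence, presence and missing information can be told apart.

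An implant date is optional. It would help only to separate same-type replacements or uncoded devices from those already in place.

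The cost is a few answer options and slightly longer data entry. Both rows already name the medical record and interview as sources, so no new source is needed. The change concerns what is recorded, not how patients are treated.

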9. RESEARCH METHODS

9.1. Study design

The study will be a non-interventional, descriptive, and longitudinal prospective study with primary data collection that involves sites/investigators. The patients must be diagnosed before enrollment with ATTR-CM and prescribed with tafamidis following indications approved by National Institute for Drug and Food Vigilance (INVIMA) in Colombia. The patients will be followed up from the index date until patient i) have deceased, ii) have decided to withdraw from the study, iii) have terminated of treatment, iv) have been lost to follow up, or, v) finalize the 24 months of following up, the event that happens first. The index date will be defined as the date for the first prescription of tafamidis.

The patients that were prescribed with tafamidis before August of 2023 will be recruited. In the cases where the patients were prescribed before starting the study, all previous information will be collected from the data provided by the patients. The quality of life will be evaluated when the patient accepts to participate and signs the informed consent.

Quality of life, adherence, concomitant treatment, hospitalization for any causes, cardiovascular functionality will be measured 24 months after the prescription of tafamidis. Twelve months before the index date, treatments, and frequency of hospitalization for any causes will be measured (Table 1).

There will be two sources of information. Clinical and demographic information and death at the baseline will be abstracted from the medical record while the data related to hospitalizations, cardiovascular functionality, quality of life will be collected directly from the patients using validated questionnaires and structured interviews. Thus, in this case the report form (CRF) will serve as a source document.

In patients who have been prescribed with tafamidis more than 1 month and have not received the drug by the HMO yet, the first time of administration of tafamidis will be considered in the analysis. It will be considered as limitation of access. Any delay of supply for treatment will be considered limitation of access which will be assessed during the follow-up.

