9.2. Setting

The study will be performed in approximately 6 Colombian Health Provider Institution (IPS, in its Spanish acronym) whose population includes patients with ATTR-CM diagnosis in the period established. These sites will be in four Colombian cities (Bogotá, Medellin, Cali, and Barranquilla) which have a cardiologist with experience in diagnostic and management of ATTR-CM. The patients can be recruited from the same site or other healthcare institutions, which the site affiliated to the study can invite to participate. In this last scenario, the patients will maintain the clinical care of the original institution, but the information of the study will be collected in the sites affiliated to the study or by their healthcare professionals through virtual interview.

Tafamidis was approved in July 2022 by INVIMA in the treatment of ATTR-CM (14), thus, the patients with diagnosis of ATTR-CM and treated with tafamidis between August 2022 to August 2023 will be invited to participate in the study. At this time, the number of patients expected to participate will be less than 50 patients considering the number of patients diagnosed with ATTR-CM. This cohort study its representative to patients in Colombia without requiring sampling method, considering the estimated number of patients diagnosed with this disease under treatment with tafamidis.

The follow-up period is 24 months since index date with measurement every three months \pm 15 days. During this period quality of life, hospitalization frequency, and death will be measured. The endpoint of the study will be death. Additionally, adherence will be measured. For the cardiovascular functionality, it will be abstracted from the medical records 6MWT and scintigraphy during the time of study.

The activities will be included in the following table.

PFIZER CONFIDENTIAL

CT24-WI-GL02-RF01 6.0 Non-Interventional Study Protocol Template For Primary Data Collection Study 01-

Aug-2023

Page 22 of 57

**CLINICAL AND MEDICAL CONTROLLED DOCUMENT (CMCD)
REQUIRED FORM/TEMPLATE**

Identifier	Version	Title	Effective Date
CT24-WI-GL02-RF01	6.0	NON-INTERVENTIONAL STUDY PROTOCOL TEMPLATE FOR PRIMARY DATA COLLECTION STUDY	01-Aug-2023

Table 1 List of activities

Visit Identifier	Screening	Month ± 15 days										End of Observation
		-12	0	3	6	9	12	15	18	21	24	
Visit Window												
Informed consent	X											
Medical history	X											
Demographic		X										
Clinical variable		X										

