9.5. Study size

Sample size is not required for being observational and descriptive study. The expected number of patients eligible for the study is close to fifty considering the number of patients identified with the diagnosis and the access to the treatment based on the national database of MiPres in Colombia in which each prescription of treatments outside of National Formulary must be registered (19).

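### Table 2 takes the tafamidis prescription (index) date and first-administration date from interview alone, which does not fit the record-based sourcing in section 9.4

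*Protocol*

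**What the plan says.** Protocol section 9.1 fixes the time origin: "The index date will be defined as the date for the first prescription of tafamidis". Section 9.2 builds the schedule on it: "The follow-up period is 24 months since index date with measurement every three months", with a tolerance of 15 days either way. The 12-month look-back (section 9.1) and persistence (section 9.3.1) also run from the index date.

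Table 2 in section 9.3 then gives the sources. The row "Date of prescription of tafamidis" reads in full "Date of prescription of tafamidis Treatment Interview ddmm/yyyy", and the first-dose row reads "Date of first administration of tafamidis Treatment Interview ddmm/yyyy". Delay of supply and its cause are also interview items. By contrast, the diagnosis date reads "Date of ATTR-CM diagnosis Clinical characteristic Medical record, Interview dd-mm-yyyy", and nearly all other baseline rows list the medical record too.

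Section 9.4 describes a different order. Treatment at baseline is abstracted from the medical record that the patient provides, and the patient confirms or completes it. During follow-up, supply problems reported by the patient are to be confirmed with the record summary; the Abstract says only that this can be done. Section 9.4 does not name the two tafamidis dates.

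Section 9.5 mentions the national MiPres database, "in which each prescription of treatments outside of National Formulary must be registered", but uses it only to estimate how many patients are eligible.

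**The concern.** Table 2 gives the date on which the study's time axis rests a weaker source than it gives to routine comorbidities. Recruitment is of patients already prescribed the drug, so a date taken at interview is a date remembered months later.

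An error in the index date moves the look-back window, the visit labels and the 24-month end, and changes the persistence count. Near the edges it can also change whether a patient falls inside the recruitment window.

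The first-administration date has a smaller role. With the prescription date it gives the delay behind the access-barrier objective, for which section 9.1 uses a threshold of one month. It also feeds two subgroup variables in section 9.7.3.2: the interval from diagnosis to start of treatment, and time on tafamidis before enrolment.

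A later analysis plan cannot repair this. If only a recalled date is captured, the documented one is not in the dataset. Section 9.1 makes the CRF the source document for data collected directly from the patient, so the monitoring in section 9.8 would have no separate document against which to check an interview-only date.

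**Working it through.** The plan states no figure for date accuracy, so there is none to reproduce. The check has three parts.

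**1. Sources side by side**

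| Item | Table 2 | Section 9.4 |
|---|---|---|
| Prescription date (index) | Interview | Baseline treatment from record; patient confirms or completes |
| First-administration date | Interview | Same general rule; date not named |
| Supply delay | Interview | Patient report, confirmed with record summary |
| Diagnosis date | Medical record, interview | Diagnosis data from record; patient confirms or completes |

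The first three rows do not agree across the two sections. The last does.

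**2. Minimum lag from prescription to interview**

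Inputs: prescription window August 2022 to August 2023 (section 9.2); start of data collection 15 November 2023 (section 6). Lag = start of data collection − prescription date, divided by 30.4375 days per month.

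- Earliest, 1 August 2022: 471 days; 471/30.4375 = 15.5 months.
- Latest, 31 August 2023: 76 days; 76/30.4375 = 2.5 months.
- Section 9.1 instead recruits those prescribed before August 2023. The latest date is then 31 July 2023: 107 days; 107/30.4375 = 3.5 months.

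These are minima, because consent after 15 November 2023 lengthens them. On that day the earliest patient has already passed the windows for months 0, 3, 6, 9 and 12 (month 12 closes at 12 × 30.4375 + 15 = 380 days, and 380 < 471). The latest patient has passed month 0 only (month 3 closes at 3 × 30.4375 + 15 = 106 days, and 106 > 76).

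**3. Illustration of recall error**

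The documents give no recall-error figure. Assume an error that is normal with mean zero and standard deviation SD. Then P(|error| > 15 days) = 2 × (1 − Φ(15/SD)).

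| Assumed SD (days) | 15/SD | Probability | Expected out of 50 patients |
|---|---|---|---|
| 7 | 2.143 | 0.032 | 1.6 |
| 15 | 1.000 | 0.317 | 15.9 |
| 30 | 0.500 | 0.617 | 30.9 |
| 45 | 0.333 | 0.739 | 36.9 |

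The answer runs from negligible to a large majority, depending wholly on an SD that nobody has measured here.

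**The case against.** The best defence is that Table 2's source column is shorthand. It lists adherence as an interview item although sections 9.3.1 and 9.4 measure it with an electronic device, and it lists hospitalisation as interview although section 9.4 confirms it with records. Section 9.6.1 says that the source is usually the chart and that CRF entries must match it. Section 9.8 plans three monitoring rounds, and section 9.9 already discloses that baseline data depend on the records and on what the patient knows. This carries weight: it shows a document that disagrees with itself, and it does not establish a design resting on unaided recall throughout. It does not remove the need to correct the row for the index date, since sites will build their source worksheets from Table 2.

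A reader might infer more than the text supports:

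- **That the first-dose date also anchors the schedule.** It does not. The visits, the look-back, the 24-month end and persistence run from the prescription date. For patients not yet supplied at enrolment, the first dose would be recorded as it happens.
- **That better records are known to be at hand.** The protocol does not say that sites have patient-level access to MiPres, which in any case registers prescriptions and not doses. It mentions no dispensing records.
- **That most index dates will be wrong.** This holds only under the larger assumed SDs. Moreover, 15 days is the tolerance for contact timing and was not set as a limit for index-date error.
- **That the primary quality-of-life measurements are compromised.** The first KCCQ is taken after signed and dated consent. An index-date error shifts all of a patient's visit labels together and leaves the intervals between KCCQ measurements unchanged.

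**Conclusion.** The point holds in a limited form. Table 2 names interview as the sole source for the date that defines the study's time axis, and for the first-administration date used for access delay and time on treatment. Section 9.4 describes record-first sourcing for baseline treatment and has supply problems confirmed with the record. The two must be reconciled.

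The lag of at least 2.5 to 15.5 months follows from the protocol's own dates (3.5 to 15.5 if section 9.1 sets the window). It assumes that data collection starts as planned. The share of dates wrong by more than 15 days, from about 3% to 74%, rests on assumed SDs and is an illustration only.

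This is an avoidable source of error that costs little to remove. It does not invalidate the design.

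**What to change.** In Table 2, set the source for the prescription date, the first-administration date and supply delay to: medical record; interview to confirm, or if the record is absent. Add one CRF field stating which source was used for each. State that the documented prescription date is the index date wherever one is available. Allow the prescription register as a source for the prescription date only, and only if sites are confirmed to have patient-level access. Align the Abstract with section 9.4 on whether supply problems will be confirmed with the record or merely can be.

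The cost is the Table 2 wording, the CRF field and some extra work. Section 9.4 already abstracts the record for baseline treatment, but section 9.2 lets patients come from other institutions, so some records will have to be requested. Where none can be obtained, the interview date stands and is flagged as such.
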